***Illness Visits: Additional nasal swab specimens for the detection of RSV and respiratory pathogens" (including COVID-19) will also be collected from participants during illness visits and 48 hours later at any other protocol specified time point in the study (Table 5-4) including medically attended visits during RSV season. If a participant visits any other non-study doctor / hospital for a serious adverse event (SAE) at any time in the study, a nasal swab sample will be obtained at the study site once the participant is discharged, if deemed appropriate by the study investigator. All the nasal swab specimens will be collected in the recommended viral transport media tube and will be stored between -60°C and -80°C until ready to ship. The requirement for an onsite or at home illness visit will be evaluated first by video call to enable remote evaluation of severity and remote management of mild (Grade 1) illness, as deemed appropriate by the study investigator.

Table of Study Procedures for Cohorts 2 and 4 – Vaccination 1 (D0 to D55)

Phase I/II Study, 6 Planned Visits, 40 (42) Non-visit Telephone Contacts, 2 Vaccinations, 4 Planned Blood Samples, 2 Planned Nasal Swabs, up to a Maximum of 12 Months of Participation per Participant

Visit (V) / Contact	Visit 01	Phone contacts 1-6	Visit 02	Phone contacts 7-16	Phone contact 17	Phone contact 18	Illness Visit(s)‡ Visit 99
Study timelines – Days (D)	D0	Daily (x6)	D7	Three times weekly (x10) between D8 and D28	D29 (+1)	D42 (+1)	Any time between Visit 01 and Visit 06
In-person visit	X		X				X
Non-visit contact*		X		X	X	X	
Informed consent	X						
Demography data	X						
Inclusion / Exclusion criteria	X						
Medical history and physical examination	X						
Vital signs†	X		X				X
COVID-19 test	X						X
Interim history			X				X
Focused clinical examination			X				X
Collection of reportable concomitant medications/ vaccinations							X
Allocation of participant number	X						
Randomization / Dose number	X						
Blood samples	BL0001						
Nasal swabs‡			NS0001				NS0001 or UN0001 to UN0000X
Vaccination (1st administration)	X						
Immediate surveillance (30 min)§	X						

Visit (V) / Contact	Visit 01	Phone contacts 1-6	Visit 02	Phone contacts 7-16	Phone contact 17	Phone contact 18	Illness Visit(s) ‡ Visit 99
Study timelines – Days (D)	D0	Daily (x6)	D7	Three times weekly (x10) between D8 and D28	D29 (+1)	D42 (+1)	Any time between Visit 01 and Visit 06
Diary Card (DC) / electronic DC (eDC) provided	DC1/eDC		DC2				

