- 6) Complete the relevant CRFs for this visit.

Visit 05: D84+8 Post-Vaccination 1 (Day 28+8 Post-Vaccination 2) Visit Procedures for Cohorts 2 and 4

- 1) Review medical history, including past and ongoing medication and immunizations since the last visit.
- 2) Perform a focused clinical examination including temperature, pulse, and respirations, EENT, respiratory, cardiac and lymphatic system.
- 3) Obtain a blood sample for serum antibodies to RSV.
- 4) Collect and review the solicited reactions and unsolicited AEs, AESIs, MAAEs and SAEs in the completed DC3 / eDC with the participant's parent / guardian / legally authorized representative. Provide MA.
- 5) If an SAE had occurred, follow the instructions in [Section 10](#) for reporting it. Remind to notify the site in case of an SAE.
- 6) Complete the relevant CRFs for this visit.

Visit 99: Illness Visits

Illness visits can be conducted remotely, as a home visit or an onsite visit depending on the judgment of the investigator. The requirement for an Illness Visit and which type of illness visit will be evaluated first by video call. The video call will be used to initially remotely evaluate the study participant's clinical status and whether the illness can be managed remotely especially for mild (Grade 1) illness. This staged management of illness visits is required during the current COVID-19 pandemic situation to limit the number of contacts between the study participant and study site staff to only those that are absolutely required. Guidelines for remote evaluation are described in the Operating Guidelines.

The timeframe after site notification in which the Illness Visit must occur, if deemed necessary by the Investigator, depends on grading of the fever and respiratory symptoms and the phase of the study. If the Illness Visit occurs on a day concurrent with a routine Study Visit when a nasal swab specimen is to be collected, the same nasal swab specimen would be used to test for respiratory pathogens. A second nasal swab should be collected 48 hours later. If the Illness Visits occurs on a day concurrent with a routine Study Visit when a nasal swab specimen is not collected, a nasal

swab specimen is required to test for respiratory pathogens. A second nasal swab should be collected 48 hours.

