During the RSV season (01 November to 31 March in the northern hemisphere and 01 May to 30 September in the southern hemisphere) or post-vaccination RSV surveillance (at least 5 months after last vaccine administration), make phone contacts every 2 weeks with the parent / guardian / legally authorized representative.

- 1) Record relevant information concerning the participant's health status including any changes in medications and immunizations on the telephone contact form.
- 2) Schedule an Illness Visit within the guidelines and stipulated time frame from the phone contact for a medically attended illness of the following types: fever, URI, LRI or otitis media. If this illness overlaps with the Acute or Post-Acute Phases, the time frames specified for the relevant Acute or Post-Acute phase should be used (see [Table 5-4](#)).

- 3) If a participant had visited any other non-study doctor / hospital for a serious adverse event (SAE) (at any time in the study), schedule a site visit once the participant is discharged to obtain a nasal swab sample for RSV viral detection and [REDACTED] for respiratory pathogens.
- 4) If an SAE had occurred, follow the instructions in [Section 10](#) for reporting it. Remind to notify the site in case of an SAE.

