An ad-hoc IDMC, which ideally will include at least 2 pediatric respiratory virus vaccine experts, will review upon request of the SMT unblinded study data. The ad-hoc IDMC will upon request review the relevant safety information and available data, including magnitude of vaccine virus shedding. If an ad hoc IDMC meeting is required, the ad hoc IDMC will review the data on safety available at that time point to determine if attributable to an etiology, a cause, or a diagnosis unrelated to the study vaccine, and if the adverse event(s) is associated with shedding of vaccine virus at the time of the event (even if another is identified). If the ad-hoc IDMC decides there is no proven causal relationship between the adverse events and study vaccine, the study can continue unchanged. Based on evaluation of the IDMC, the Sanofi Pasteur SMT will decide if there is a causal relationship between the adverse event and the study vaccine, then SMT will decide whether to:

- Conduct internal signal detection processes (SOP # RDWIN-000390)
- Escalate validated signals to PSB as needed
- Continue the trial
- Modify the trial design (with PSB and ad-hoc IDMC input) or,
- Stop the trial (with PSB and ad-hoc IDMC input).

The following safety parameters will be assessed as part of the early safety review:

- Immediate reactions
- Solicited respiratory and systemic reactions
- Unsolicited reactions i.e., AEs reported as related by the Investigator
- SAEs, MAAEs and AESIs

Enrollment will not be paused during the review. The data will be examined for the following:

- 1) Any deaths, regardless of causality.
- 2) Any vaccine related SAEs.
- 3) Grade 3 fever reported in > 2 participants.
- 4) Any Grade 3 or above solicited adverse events other than fever.
- 5) >1 participant experiencing lower respiratory tract illness of >Grade 2 DAIDS scale (except for wheeze by Brighton Collaboration Severity Scale) during the acute phase (i.e., within 28 days post-vaccination).
- 6) Any participant experiencing an AESI of Grade 3 or above by DAIDS scale (except for wheeze by Brighton Collaboration Severity Scale), including lower respiratory tract illness during the acute phase (i.e., within 28 days post-vaccination).
- 7) >1 participant with a Grade 3 unsolicited AE during the acute phase (i.e., within 28 days post-vaccination).
- 8) Any other pattern of research laboratory values or clinical symptoms other than fever that is considered a significant safety issue by the Investigator.

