9.3.4 Efficacy

9.3.4.1 Efficacy Endpoints

The exploratory endpoints for the evaluation of efficacy assessed through the RSV season or post-vaccination surveillance period are:

- RSV medically attended acute respiratory illness (RSV MAARI)
- RSV medically attended acute lower respiratory illness (RSV MAALRI)
- A diagnosis of RSV MAARI requires a respiratory sample positive for RSV by [REDACTED] AND documented physical exam findings of respiratory tract illness including any of the following:
 - Fever
 - Acute otitis media
 - Upper respiratory tract illness:
 - Runny nose/rhinorrhea
 - Pharyngitis
 - Cough without LRI
 - Lower respiratory tract illness (see MAALRI below)
- A diagnosis of RSV MAALRI (a subset of MAARI) requires a respiratory sample positive for RSV by [REDACTED] AND documented physical exam findings of lower respiratory tract illness including any of the following:
 - Stridor
 - Rales
 - Tachypnea
 - Acute wheeze
 - Pneumonia
 - Laryngotracheobronchitis

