9.3.4.2 Efficacy Assessment Methods

[figure not shown]
The method for the exploratory efficacy endpoints is the [REDACTED], an automated qualitative nucleic acid multiplex *in vitro* diagnostic test designed to simultaneously detect and identify multiple respiratory viral and bacterial nucleic acids in NS samples.

[REDACTED] Method:

The ePlex system which is used to run the [REDACTED] is a closed system that automates all aspects of nucleic acid testing including extraction, amplification, and detection. Electrowetting or digital microfluidics use electrical fields to manipulate droplets on the surface of a

hydrophobically coated printed circuit board (PCB). Samples and reagents are moved in a programmable fashion in the ePlex cartridge to complete all portions of the sample processing. Nucleic acid extraction from biological samples occurs within the cartridge via cell lysis, followed by nucleic acid capture onto magnetic beads and release for [REDACTED] amplification. Thereafter, exonuclease digestion creates single-stranded DNA in preparation for eSensor detection. eSensor technology is based on the principles of competitive DNA hybridization and electrochemical detection, which is highly specific and is not based on fluorescent or optical detection. Competitive DNA hybridization: the single-stranded target DNA binds to a complementary, single-stranded capture probe, immobilized on the working gold electrode surface. The single-stranded signal probes (labeled with electrochemically active ferrocenes) bind to a specific target sequence/region adjacent to the capture probe. Simultaneous hybridization of the target to signal probes and capture probe is detected by alternating current voltammetry (ACV). Each working electrode on the array contains specific capture probes, and the sequential analysis of each electrode allows for the detection of multiple analyte targets.

The [REDACTED] is a qualitative assay. It will only indicate the presence or absence of a viral or bacterial target in a nasal swab sample collected in viral transport medium (VTM) and will not be used to calculate a viral titer. The [REDACTED] can detect and distinguish between sixteen respiratory viral targets and two respiratory bacterial targets as shown in Table below.

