4.4.3 Efficacy

The following events will be collected in the database during illness visits:

- Fever
- Acute otitis media
- Upper respiratory tract illness:
 - Rhinorrhea
 - Nasal congestion
 - Pharyngitis
 - Cough without LRI
- Lower respiratory tract illness
 - Stridor
 - Rales
 - Tachypnea
 - Acute wheeze
 - Pneumonia
 - Laryngotracheobronchitis

A diagnosis of RSV MAARI requires the documentation of any of the events described above, associated with a respiratory sample positive for RSV by [REDACTED].

A diagnosis of RSV MAALRI (a subset of MAARI) requires the documentation of any of the lower respiratory tract illness events described above, associated with a respiratory sample positive for RSV by [REDACTED].

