5.1.3 Statistical Methods for Exploratory Objectives

Safety

Solicited ARs, unsolicited AEs (including SAEs), MAAEs and AESIs will be summarized. Analyses described in Section 5.1.1.2 will be presented by vaccine group after each and any vaccination by baseline serostatus.

Immunogenicity

Similar analyses as described as for secondary immunogenicity objectives will be performed on exploratory immunogenicity endpoints.

Analyses on RSV A and RSV B serum anti-Gcc IgG antibody responses planned in the protocol will finally not be produced for this study, please refer to section 5.7 for the rationale.

Efficacy

RSV Medically attended respiratory illness collected during the RSV season will be summarized. The main parameters will be described with 95% CI. At least the following parameters will be presented by vaccine group:

- RSV medically attended acute respiratory illness (RSV MAARI) by SOC and PT, intensity, time of onset, and duration
- RSV medically attended lower respiratory tract illness (RSV MAALRI) by SOC and PT, intensity, time of onset, and duration
- Vaccine Efficacy (VE)

The VE of RSVt vaccine (low dose or high dose, as applicable) will be estimated for each endpoint as follows:

$$VE = 1 - \frac{C_{RSV}/N_{RSV}}{C_P/N_P}$$

where:

- C_{RSV} and C_P are the numbers of RSV MAARI / RSV MAALRI cases meeting the considered definition in the RSV (low dose or high dose) and Placebo groups, respectively.
- N_{RSV} and N_P are the numbers of participants in the RSV (low dose or high dose) and Placebo groups, respectively.

The CI will be calculated using the exact method conditional on the total number of cases in both groups described by Breslow & Day (2).

Let $q = \frac{C_{RSV}}{C_{RSV}+C_P}$, the proportion of cases belonging to RSV group (low dose or high dose) among the total number of cases in the considered RSV vaccine group and Placebo group. Given the total number of cases, C_{RSV} has a binomial distribution ($C_{RSV}+C_P$, q). Thus, a CI for q may be constructed using the exact Clopper-Pearson method for binomial proportions (1).

As $\frac{q}{1-q} = \frac{C_{RSV}}{C_P}$, the VE estimate given above may be restated as follows:

$$VE = 1 - \frac{C_{RSV}/N_{RSV}}{C_P/N_P} = 1 - \frac{N_P}{N_{RSV}} \times \frac{q}{1-q}, \text{ which is a strictly decreasing function of } q.$$

Finally, for each efficacy endpoint, a CI of the VE will be constructed based on the CI of q .

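### A child hospitalised away from the study site with confirmed RSV may not count as an RSV MAARI/MAALRI case, because the study swab waits for discharge and neither document provides for a hospital result

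*Protocol*

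**What the plan says.** **Swab after an outside SAE.** The illness-visit footnotes to the Protocol's Tables of Study Procedures (Cohorts 1 and 3, and both tables for Cohorts 2 and 4) state that "a nasal swab sample will be obtained at the study site once the participant is discharged, if deemed appropriate by the study investigator". SAP Tables 3.1 to 3.3 repeat this. Protocol 5.1.4.2, on telephone contacts during the RSV season or post-vaccination surveillance, tells the site to "schedule a site visit once the participant is discharged to obtain a nasal swab sample for RSV viral detection" and has no discretion clause. Table 5-4 in Protocol 5.1.4.1 sets an illness visit within 2 days for an SAE of any grade in every phase. The text before that table again leaves the visit to judgment: "The timeframe after site notification in which the Illness Visit must occur, if deemed necessary by the Investigator".

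**Case definition.** Protocol 9.3.4.1: "A diagnosis of RSV MAALRI (a subset of MAARI) requires a respiratory sample positive for RSV by" an assay whose name is blacked out, together with documented examination findings of lower respiratory illness. MAARI has the same structure with a wider list of signs. Protocol 9.3.4.2 begins "The method for the exploratory efficacy endpoints is the" and describes one automated multiplex panel run on nasal swab samples. SAP 4.4.3 introduces the list of qualifying signs with "The following events will be collected in the database during illness visits".

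**Analysis.** SAP 5.1.3 computes VE from "cases meeting the considered definition". Protocol 12.3.3 and SAP 5.3.3 do not impute missing efficacy data. Protocol 5.1.1 uses a post-season 4-fold antibody rise to reveal wild-type infection that surveillance missed, but this is not part of the case definition.

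**The concern.** The exploratory efficacy objective (Protocol 2.3) is to describe how often RSV illness occurs and how severe it is. Under these rules, the illness most likely to be missed is the illness that put a child in a hospital outside the study. By discharge the child may have cleared the virus, and nothing in either document says that the hospital's own positive test can stand in for the study swab. The event stays in the SAE tables but can be absent from RSV MAARI, RSV MAALRI and VE. With groups of 120, 100 and 80, a few such absences could visibly move the severity table and the VE estimate.

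**Working it through.** **1. Plan's own figures.** The documents give no figure for RSV case capture, attack rate, share hospitalised or expected VE. Their only design figures are 95% chances of seeing an event (Protocol 12.5). These reproduce, 1 − 0.97^100 = 95.2% and 1 − 0.9625^80 = 95.3%, but do not bear on this point.

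**2. Tracing one child through the rules.** A child is admitted to a non-study hospital in the surveillance window and tests RSV-positive there.
- *Study swab before admission?* If an illness visit took place, yes, and the child can be a case. If not, go on.
- *Study swab during the stay?* The footnotes and 5.1.4.2 both wait for discharge. Table 5-4's 2 days would fall within any longer stay, and the documents do not say which rule governs.
- *Study swab after discharge?* Scheduled under 5.1.4.2; discretionary under the footnotes.
- *If that swab is negative?* No passage provides for the hospital result, so the laboratory criterion is not clearly met.
- *Signs?* Protocol 9.3.4.1 asks only that they be documented. SAP 4.4.3 is narrower and refers to illness visits.

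**3. Delay.** The swab comes at least a full hospital stay after admission. If the parent does not report and the site learns of the event at the next 2-weekly call, the delay can reach 14 + 2 = 16 days for a stay of up to 14 days.

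**4. Share of cases lost (assumed inputs).** Let h be the share of MAALRI admitted elsewhere, b the share of those already swabbed positive before admission, t the share swabbed after discharge and s the share of those still positive.

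Loss = h × (1 − b) × (1 − t × s)

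Take h = 20–40%, t = 50–100%, s = 50–80%. With b = 0:
- low end: 0.20 × (1 − 1.0 × 0.8) = 4%
- high end: 0.40 × (1 − 0.5 × 0.5) = 30%

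Any pre-admission capture lowers both, and b = 1 gives 0. None of these inputs comes from the documents.

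For small counts, if each hospitalised case is missed with probability m, the chance of losing at least one of k is 1 − (1 − m)^k. For m = 10–50% this is 19–75% with k = 2 and 34–94% with k = 4.

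**5. Effect on VE (assumed counts).** The SAP formula is VE = 1 − (N_P/N_RSV) × q/(1 − q), with q = C_RSV/(C_RSV + C_P) and Clopper-Pearson limits on q. Start from 12/120 placebo and 5/100 low-dose cases:

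| Cases missed | Placebo | Low dose | VE (95% CI) |
|---|---|---|---|
| none | 12 | 5 | 50% (−53 to 86) |
| 1 placebo | 11 | 5 | 45% (−70 to 85) |
| 2 placebo | 10 | 5 | 40% (−93 to 84) |
| 4 placebo | 8 | 5 | 25% (−160 to 81) |
| 2 in each group | 10 | 3 | 64% (−40 to 94) |

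**6. Direction in expectation.** If the chance of loss is the same in both groups and efficacy does not depend on severity, expected VE is unchanged and only precision suffers. If VE is 80% against hospitalised and 50% against other cases, and hospitalised cases are 10–40% of placebo cases, true overall VE runs from 1 − (0.9 × 0.5 + 0.1 × 0.2) = 53% to 1 − (0.6 × 0.5 + 0.4 × 0.2) = 62%. It falls to 50% if every hospitalised case is missed. If vaccinees clear virus sooner, the error goes the other way.

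**The case against.** The case against is strong on several points.

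- *A reader might infer that in the RSV season the swab depends on the investigator's wishes.* Protocol 5.1.4.2, which covers that window, has no such clause. The footnotes do, so the passages conflict. The post-discharge timing is common to both.
- *Other routes to a swab exist.* Illness visits require one, with a second 48 hours later, and may be made at home. Table 5-4 allows 3 days for medically attended respiratory or febrile illness above Grade 2 in season, and parents are asked to report SAEs at once. This stands: a child swabbed before admission is captured.
- *A reader might infer that the plan bars hospital results.* It does not say so. The assay name is blacked out in the public copy, which is no fault of the plan, and a hospital test by the same method might qualify. What stands is that no passage provides for it.
- *Signs need not be present at the swab.* Protocol 9.3.4.1 can be read to admit hospital-recorded findings; only SAP 4.4.3 points elsewhere.
- *A reader might extend the point to wild-type RSV exclusion.* Protocol 12.2.1 and 12.2.3 speak of laboratory-confirmed or diagnosed infection without naming the study assay, so the extension is unsupported.
- *A reader might say that the ad-hoc IDMC cannot judge whether an event is "associated with shedding of vaccine virus at the time of the event".* That goes too far. Protocol 9.1.1.1 ties the 28-day Acute Phase to the duration of shedding, so a later swab may still detect vaccine virus.
- *Standing of the endpoint.* It is exploratory and descriptive, and dose selection (Protocol 5.1.2) rests on safety, infectivity, shedding and immunogenicity. That limits the consequence but does not remove the gap.

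**Conclusion.** The point holds as a gap in case ascertainment. A child admitted elsewhere with hospital-confirmed RSV, not swabbed before admission and negative after discharge, may not count as RSV MAARI or MAALRI, and such loss is concentrated at the severe end.

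Its size cannot be determined from the documents. The 0 to 30% range rests wholly on assumed inputs. A reader might also infer that VE is inflated, but the documents do not support a direction: the illustrations move it up, down or not at all. The practical effect is confined to the frequency and severity of RSV illness and to exploratory VE; hospitalised events remain in the SAE analysis. A correction is worthwhile because it is cheap and because the swab rules disagree with one another in any case.

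**What to change.** 1. **SAP 4.4.3 and Protocol 9.3.4.1.** State that listed signs, or a lower respiratory illness diagnosis, documented in the hospital record meet the clinical criterion. Record any documented RSV-positive result from the treating hospital, with a flag for its source.
2. **SAP 5.1.3.** Report RSV MAARI, RSV MAALRI and VE twice: study assay only, and with hospital-confirmed cases added. Show events within 28 days of a dose separately, because local tests may not distinguish vaccine virus from wild-type virus.
3. **Reconcile** the procedure-table footnotes (Protocol, and SAP Tables 3.1 to 3.3), Table 5-4 and Protocol 5.1.4.2 on whether and when the swab is taken for respiratory or febrile SAEs treated elsewhere. Simply striking the discretion clause would be too broad, since it covers every SAE, including non-respiratory ones.

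**Cost.** Wording changes and one CRF field for the source of the RSV result. Hospital reports and discharge summaries are already sought for SAEs (Protocol 9.1.1.3.3 and Section 10). Local assays differ in performance; the flag and the two-way presentation handle this and keep the study-assay definition intact.
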